## 4 STUDY OBJECTIVES

The objective of this study is to evaluate the safety and effectiveness of the size 23 mm Magna mitral valve in subjects with mitral heart valve disease requiring

replacement with a valve. Data collected in this study will be used to support the premarket application supplement to P860057 for approval of the 23 mm size in the United States. This study may also be used to support device approval in other countries as applicable.

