## 5 STUDY DESIGN

This is a prospective, non-randomized, multi-site descriptive study. A minimum of 15 and up to 20 subjects will be implanted at a minimum of 2 and up to 8 participating investigational sites, within the US and internationally. Subject participation will last for 5 years. Subjects will be assessed for clinical follow-up at the following intervals: pre study procedure, at implant, index hospitalization discharge or within 30 days of implant, whichever comes first, 6 months post

procedure, 1 year post procedure, and annually thereafter until 5 years post procedure or death, whichever occurs first.

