#### 8.9 MISSED SUBJECT VISITS

The Investigator(s) will make every attempt to follow the subjects and subjects will be encouraged by the Investigator(s) to report any address or telephone number changes to the implanting site. They will also be informed of the importance of returning for scheduled follow-up visits even if they are not having any problems.

If a subject cannot be reached for a follow-up visit, the Investigator will document on the CRF, the efforts undertaken to contact the subject or the subject's primary health care provider. These efforts should include 3 attempts of telephone contacts at separate dates and times, and a registered letter before the end of the follow-up window. If a subject cannot be reached for the follow-up visit and misses the scheduled visit, the visit will be recorded as a missed visit on the date of last attempted contact. Subjects who miss a visit will not be considered withdrawn. At the next visit interval, the Investigator and/or designee will attempt to contact the subject again for follow-up. Should this attempt to contact the subject fail, a family member should be contacted in addition to the subject. Subjects who miss 2 sequential follow-up visits will be considered lost to follow-up at the second missed visit and exempt from future study follow-up visits. After the subject is terminated from the study, the Investigator will attempt to determine if the subject is alive, including searching national mortality registries as permitted by local laws.

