### **ANALYSIS POPULATION**

The primary safety and effectiveness analyses will include all the implanted subjects. All the data collected up to the point of the explant or expirations will be included in the safety and effectiveness analyses.

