#### **11.1 SAFETY ANALYSIS**

##### **11.1.1 SAFETY ENDPOINTS**

The following adverse events will be reported for the safety analysis:

- Thromboembolism
- Valve thrombosis
- All hemorrhage
- Major hemorrhage
- All perivalvular leaks
- Major perivalvular leak
- Endocarditis
- Hemolysis
- Structural valve deterioration
- Non-structural valve dysfunction

- Reoperation
- Explant
- Death
- Valve-related death.

Rates of the above referenced adverse events within the early (within 30 days of implant) post-operative period, calculated as the number of events divided by the number of subjects, will be reported.

The calculation of late rates and standard errors for the safety endpoints will be based on actuarial (Kaplan-Meier) methods in addition to rates based on cumulative patient-years.

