**Table 8: Times to Re-operation, Explants and Deaths**

Event	Starting point	End point
Re-operation	Implant Date	Re-operation Date*
Explant	Implant Date	Explant Date*
Death	Implant Date	Expiration Date

\* Time to first explant or re-operation will be calculated for those subjects requiring multiple explants or re-operations. Analyses of “time to explants” and “time to re-operation” will also be stratified by outcomes--fatal versus non-fatal events.

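### In the visible safety plan, late rates carry only a Kaplan-Meier standard error, which is 0 for an event-free endpoint, and early and patient-year rates carry no uncertainty measure

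*Combined protocol and SAP*

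**What the plan says.** Sections 4.1 and 11.1.1 list the same 14 safety endpoints and the same rules for summarising them.

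- **Early rates (within 30 days of implant)** are "calculated as the number of events divided by the number of subjects, will be reported". No standard error or interval is named.
- **Late rates:** "The calculation of late rates and standard errors for the safety endpoints will be based on actuarial (Kaplan-Meier) methods".
- **Patient-year rates** are given "in addition to rates based on cumulative patient-years". Only the rates are named.

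Section 11.1.1.1 ("Table 8: Times to Re-operation, Explants and Deaths") starts the clock at implant for re-operation, explant and death. No time origin is stated for the other endpoints. Section 11 describes the analysis as descriptive, and no visible section plans a confidence interval for a safety rate. The means, standard deviations and ranges in Section 11.2.1.1 are for echocardiographic variables.

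On size, Section 5 says: "A minimum of 15 and up to 20 subjects will be implanted", each followed for 5 years. On use, Section 4 says: "Data collected in this study will be used to support the premarket application supplement to P860057". Section 11 adds a general comparison with Model 6900P data from Protocol 98-1. Under General Statistical Methods, the synopsis names the format used for an earlier valve approval as a guide to data presentation. That format is not reproduced in the documents.

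**The concern.** The plan intends to report precision, since it commits to standard errors. But the one measure it names gives no information when events are absent. The usual Kaplan-Meier standard error is 0 on a curve with no event, however few subjects lie behind it. A value of 0 is correct as a statistic, but it does not describe what 15 to 20 subjects can exclude.

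Set beside the Protocol 98-1 data in a premarket supplement, a line showing 100% freedom with standard error 0 can be read as a precise result when it is an imprecise one. Beside the early and patient-year rates there would be no measure at all.

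**Working it through.** The plan states no precision figure, sample-size calculation or event rate, so there is nothing of its own to reproduce. The check asks what the stated rule would print and what the same data would support.

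**Inputs.** n = 15 or 20 (Section 5). Follow-up is 5 years (Section 5). The early period is 30 days (11.1.1). Assumptions of this review: two-sided 95% level, and complete follow-up unless stated.

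**1. Kaplan-Meier standard error with no event.** Greenwood: SE = S × √Σ[d / (r(r − d))]. With no event every d is 0, so S = 1 and SE = 0 at any n. The Peto form, S × √[(1 − S)/r], is also 0 at S = 1. The plan does not say which form it uses; both give 0.

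**2. When this occurs.**
- Re-operation, explant and death start at implant (Table 8), so the standard error is 0 only if there is no event at all. With one early event and no censoring, SE = √[p(1 − p)/n]: 6.4 points at p = 14/15 and 4.9 points at p = 19/20.
- For endpoints with no stated origin, a curve starting at day 30 gives 0 when there is no late event; a curve starting at implant gives 0 only when there is no event at all.

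**3. Early risk, zero events.** Clopper-Pearson upper limit = 1 − 0.025^(1/n).
- 0/15: 1 − 0.025^(1/15) = 21.8%
- 0/20: 1 − 0.025^(1/20) = 16.8%

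**4. Late rate, zero events.** Late patient-years = n × (T − 30/365.25). Exact Poisson upper limit = −ln(0.025)/PY = 3.689/PY.

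| Case | PY (n = 15) | Upper limit per 100 PY | PY (n = 20) | Upper limit per 100 PY |
|---|---|---|---|---|
| 5 years, complete | 73.8 | 5.0 | 98.4 | 3.8 |
| 5 years, 20% of PY lost (assumed) | 59.0 | 6.3 | 78.7 | 4.7 |
| 1 year, complete | 13.8 | 26.8 | 18.4 | 20.1 |

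Complete follow-up is the best case. The Analysis Population text says: "All the data collected up to the point of the explant or expirations will be included in the safety and effectiveness analyses", and Section 8.9 says: "Subjects who miss 2 sequential follow-up visits will be considered lost to follow-up at the second missed visit". Explants, deaths and losses therefore all shorten the observed time. The 20% loss only illustrates this; the documents give no figure.

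**5. How likely an empty curve is.** For a true cumulative risk p, P(no event) = (1 − p)^n. The values of p are assumptions.

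| p | n = 15 | n = 20 |
|---|---|---|
| 1% | 86% | 82% |
| 2% | 74% | 67% |
| 5% | 46% | 36% |
| 10% | 21% | 12% |

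In terms of a constant late rate with complete follow-up, zero late events is more likely than not below ln(2)/PY: 0.94 (n = 15) or 0.70 (n = 20) per 100 patient-years.

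**The case against.** The strongest reply is that this is a reporting preference in a descriptive study. There is no hypothesis, margin or success criterion, and no stated rule uses the standard error. That stands, and it limits the point to reported precision. It does not remove it, because an interval is itself a descriptive statistic.

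Second, the presentation format named in the synopsis may already show limits. This also stands. A reader might infer that the final report will lack intervals; the documents do not support that. They show only that 4.1 and 11.1.1 do not provide for them.

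Third, early and patient-year rates with no error measure cannot show false precision, and a reader given 0/15 can derive the limit. This is partly right. The misleading output is the standard error of 0; for the other two rates the gap is an omission. Deriving late limits also needs patient-years and numbers at risk, and the visible plan does not commit to showing numbers at risk.

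Fourth, the late-rate sentence could be read loosely as giving standard errors to the patient-year rates too. That would not help at zero events: the usual form, √(events)/PY, is also 0.

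A reader might also infer that most of the 14 endpoints will be affected, or that the standard error fails even when events occur. The documents give no event rates, so the first cannot be known. For the second, the plan proposes no interval built from the standard error, so there is none to criticise.

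**Conclusion.** The point holds for the visible text. An endpoint with no event on its curve would be reported as 100% freedom with standard error 0. Yet zero early events leave risks up to 21.8% (n = 15) or 16.8% (n = 20) unexcluded, and zero late events leave rates up to 5.0 or 3.8 per 100 patient-years.

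The late figures assume complete five-year follow-up and a constant rate with independent events; with losses the limits are wider. All figures use a two-sided 95% level, which the plan does not set.

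The consequence is misstated precision in the safety tables and in the general comparison with Protocol 98-1. No test, sample-size claim or decision rule is affected, and the standard error of 0 is not a calculation error. The point should be fixed because the better summary needs no new data and changes what a reader can conclude from zero events.

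**What to change.** Amend Sections 4.1 and 11.1.1 as follows.

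1. **Early rates:** report subjects with at least one event divided by subjects implanted, with a Clopper-Pearson 95% interval. List the event count separately if subjects have repeat events. The planned numerator counts events, so a binomial interval would otherwise belong to a different quantity from the rate beside it.
2. **Patient-year rates:** add exact Poisson 95% limits from the observed patient-years, noting the constant-rate and independence assumptions.
3. **Kaplan-Meier estimates:** state the time origin of each curve, show the number at risk, and give an interval that does not collapse at zero events, for example beta product, or the exact binomial limit when there is no censoring. Do not show a standard error of 0 as the only precision measure.

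If the format cited in the synopsis already gives such limits, a sentence in 11.1.1 saying so is enough.

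The cost is a few sentences and a small amount of programming. Whether the software named in Section 11.3 offers beta-product limits directly was not checked. The downside is that the reported intervals will be wide.

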#### 11.1.1.1 Time to Death, Re-operation, and Explant

Times to re-operation, explants and death are listed in Table 8 below:

**Table 8: Times to Re-operation, Explants and Deaths**

Event	Starting point	End point
Re-operation	Implant Date	Re-operation Date*
Explant	Implant Date	Explant Date*
Death	Implant Date	Expiration Date

\* Time to first explant or re-operation will be calculated for those subjects requiring multiple explants or re-operations. Analyses of “time to explants” and “time to re-operation” will also be stratified by outcomes--fatal versus non-fatal events.

#### 11.1.1.2 Blood Data

Blood data (red blood count, white blood count, hematocrit, hemoglobin, platelet count, and plasma free hemoglobin) will be collected preoperatively, at 6-months and annually post implant. This blood data will support the absence / presence of

related adverse events, in particular hemolysis. Data will be reported as the percent of subjects with results within the normal ranges at each time interval. The percent of subjects with hemolysis at each interval will also be reported.

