#### 4.1 SAFETY ENDPOINTS

Safety Endpoints include the following:

- Thromboembolism
- Valve thrombosis
- All hemorrhage
- Major hemorrhage
- All perivalvular leak
- Major perivalvular leak
- Endocarditis
- Hemolysis
- Structural valve deterioration
- Non-structural valve dysfunction
- Reoperation
- Explant
- Death
- Valve-related death

Rates of the above referenced adverse events within the early (within 30 days of implant) post-operative period, calculated as the number of events divided by the number of subjects, will be reported.

The calculation of late rates and standard errors for the safety endpoints will be based on actuarial (Kaplan-Meier) methods in addition to rates based on cumulative patient-years.

Blood Data to evaluate valve-related hemolysis collected preoperatively, at 6-month, 1-year, and every yearly follow-up visit will be analyzed and presented by time period.

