#### 8.5 BASELINE – PRIOR TO PROCEDURE

A baseline evaluation is to be conducted within 1 month prior to device implant.

The baseline evaluation will include:

1. History and physical examination
2. Screening for clinical inclusion and exclusion criteria
3. Baseline blood studies (Complete blood count and Plasma Free Hemoglobin)
4. Baseline echocardiography per protocol \*\*
5. Baseline 12 lead electrocardiogram
6. NYHA Functional Class
7. Quality of Life Survey (EQ-5D)

\*\* Baseline echocardiography must be completed within 6 months of study procedure.

Baseline information, findings, and results to be recorded are identified in Table 3.

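### Blood analytes are summarized only as the share in normal range at each visit, not paired with each subject's preoperative value, so newly abnormal results can be offset by recoveries in others; the hemolysis endpoint is reported separately

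*Combined protocol and SAP*

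**What the plan says.** Section 8.5 includes "Baseline blood studies (Complete blood count and Plasma Free Hemoglobin" in the baseline evaluation. Section 8.7.3 and its Table 7 repeat the same tests at 6 months, 1 year and annually to 5 years.

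Section 4.1 gives the purpose and the presentation: "Blood Data to evaluate valve-related hemolysis collected preoperatively, at 6-month, 1-year, and every yearly follow-up visit will be analyzed and presented by time period". Section 11.1.1.2 says the results bear on whether there are "related adverse events, in particular hemolysis", and it specifies two summaries. The first covers the analytes: "Data will be reported as the percent of subjects with results within the normal ranges at each time interval". The second covers the condition: "The percent of subjects with hemolysis at each interval will also be reported".

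Hemolysis is also one of the listed safety endpoints in Section 11.1.1. Its early rate, for the first 30 days, is "calculated as the number of events divided by the number of subjects, will be reported". For later follow-up, "The calculation of late rates and standard errors for the safety endpoints will be based on actuarial (Kaplan-Meier) methods", alongside rates per patient-year. Section 10 starts adverse event collection at implant.

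Other variables get a within-subject comparison. Section 11.2.1.1 plans change from baseline for the continuous echo variables, and Section 11.2.1 counts subjects whose NYHA class improved, stayed the same or worsened. Section 11.1.1.2 plans nothing of this kind for the blood analytes.

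**The concern.** A valve effect on red cells is a change after implant in a given subject. The percentage in range at a visit is a marginal figure: it mixes subjects who were abnormal before surgery with those who became abnormal afterwards. Subjects who recover after surgery raise it, and subjects with new abnormalities lower it by the same amount each. The two can cancel.

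Two further losses follow from the same choice. Reducing a continuous value to in or out of range hides a rise in plasma free hemoglobin that stays inside the range. In addition, no denominator is stated, although subjects leave the count through explant or death (Analysis Population, Section 11) or after two consecutive missed visits (Section 8.9).

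What is at stake is the usefulness of the laboratory data as a check on event reporting. Hemolysis events depend on investigators identifying and reporting them, and the text available gives no laboratory criterion for hemolysis (one may sit in removed material). The blood draws are the measured evidence alongside those reports. As specified, their summary does not count the subjects whose results turned abnormal after implant.

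**Working it through.** The plan gives no figure to reproduce. The study is descriptive (Section 11), with 15 to 20 implanted subjects (Section 5) and no stated preoperative rate for any analyte. The check therefore asks what the planned percentages can reveal, over a range of assumed rates.

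**Setup.** Of n subjects with results at both times, let a be normal preoperatively and b normal at a visit. Let x be the number going from normal to abnormal and r the number going from abnormal to normal. Then

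b = a − x + r, with 0 ≤ x ≤ a and 0 ≤ r ≤ n − a.

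The planned summary fixes only a and b. It follows that

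max(0, a − b) ≤ x ≤ min(a, n − b).

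**One point on the range.** Take n = 20 and a = 14 (70%). Suppose 4 of the 6 abnormal subjects recover and 4 of the 14 normal subjects become abnormal. Then b = 14 − 4 + 4 = 14, again 70%. The report shows no movement, while 4/14 = 29% of those normal before surgery are newly abnormal. The 4-for-4 exchange is chosen for illustration. The bounds below do not depend on it.

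**Bounds when the share normal is the same before and after (a = b).** The lower limit is 0 and the upper limit is min(a, n − a).

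| n | Normal at both times | Possible newly abnormal |
|---|---|---|
| 20 | 10 (50%) | 0–10 |
| 20 | 12 (60%) | 0–8 |
| 20 | 14 (70%) | 0–6 |
| 20 | 16 (80%) | 0–4 |
| 20 | 18 (90%) | 0–2 |
| 20 | 20 (100%) | 0 |
| 15 | 8 (53%) | 0–7 |
| 15 | 10 (67%) | 0–5 |
| 15 | 12 (80%) | 0–3 |
| 15 | 14 (93%) | 0–1 |
| 15 | 15 (100%) | 0 |

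A shift table reports x directly, so each range becomes a single number.

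**Denominator.** As an assumed illustration, start from 14/20 = 70% normal and let 3 of the 6 abnormal subjects leave follow-up. The percentage becomes 14/17 = 82% with nobody improving.

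**Does this carry over to hemolysis?** Apply the same bound to the percentage with hemolysis per interval, with h subjects affected both preoperatively and at the visit. The number of new cases lies between 0 and h. If h = 0, nothing is hidden. If h is 1, 2 or 3, up to 1, 2 or 3 cases could be new. The event rates in Section 11.1.1 count events after implant, so another subject's recovery cannot reduce them.

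**The case against.** The strongest reply is that hemolysis does not depend on the in-range percentages. It has a percentage of its own in the next sentence of Section 11.1.1.2, an early rate, and late Kaplan-Meier and patient-year rates, all within a system that collects events from implant. The adverse event definition in Section 10.1 takes in abnormal laboratory findings, and Section 13.1 has at least one committee member review each event. Kaplan-Meier estimation also allows for unequal follow-up. This stands, and it limits the point to the laboratory tables.

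A reader might infer that the plan disregards the preoperative draw, or that new hemolysis could go uncounted because others recover. The documents support neither reading. Sections 4.1 and 11.1.1.2 present the preoperative results as a time period, so a net fall in the share normal would be visible; what is missing is the pairing. Post-implant hemolysis events are counted on their own.

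It can also be said that the preoperative rates are assumed. They are, and if nearly all subjects are normal before surgery the effect nearly vanishes, which may be so for plasma free hemoglobin. That cannot be presumed for every analyte, because the exclusion criteria in Section 6.3 do not bar anemia or preoperative hemolysis and the device may replace a failed prosthesis.

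Finally, the Synopsis refers to the data format of an earlier approval, and the case report forms are redacted. Shift displays or listings may exist there. Section 11.1.1.2 does not commit to them.

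**Conclusion.** The point holds for the laboratory summary. Section 11.1.1.2 commits each blood analyte to a marginal percentage in range and does not link a subject's later results to that subject's preoperative result, although the plan makes such a link for echo variables and NYHA class. With an assumed equal share normal before and after in 20 subjects, the planned figure leaves 0 to 6 newly abnormal at 70%, 0 to 2 at 90% and none at 100%.

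It does not extend to the hemolysis event rates. The only residual weakness in hemolysis reporting is that its per-interval percentage is also marginal, which matters only if some subjects have hemolysis before surgery. No endpoint, sample size or decision rule changes. This is an inexpensive improvement to a supportive analysis.

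**What to change.** In Section 11.1.1.2, add for each analyte and each follow-up visit:

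- a shift table of preoperative status (in or out of range) by status at the visit;
- the paired change from the preoperative value (median and range) among subjects with both values;
- the denominator for each table, and the number with a missing value at either time.

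Report the number of subjects whose plasma free hemoglobin is newly out of range after implant, labeled as supportive. It should sit beside the hemolysis endpoint and not replace it as the main result. The existing in-range percentages can stay.

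The cost is a few extra tables on data already collected in 15 to 20 subjects, with no added visits or blood draws.

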## 11.2 EFFECTIVENESS ANALYSIS

### 11.2.1 EFFECTIVENESS ENDPOINTS

Mean effective orifice area (EOA) at 1 year post-implant will be reported. The pre-procedure and 1 year post-procedure NYHA distribution (numbers and percentages of subjects) will be tabulated. Number and percentage of subjects in NYHA functional class I or II at 1 year post-implant will be reported. NYHA functional class will be obtained at each follow-up time-point, and the numbers and percentages of subjects who have improved in class, not changed in class, and worsened in class will be reported.

